Neonatal clinical care seeking is inadequate, often delayed, and requires more real-time support. Many newborns continue to die at home without health care services being sought (18). The reasons are multifactorial, at the societal, health system, and family levels. Strategic Objective 4 of the Every Newborn Action Plan is to “harness the power of parents, families and communities” by engaging them to seek care throughout pregnancy, birth and the first days and weeks of their children’s lives. Improved identification and management of neonates with potentially life-threatening illness at home is critically needed to significantly reduce neonatal mortality (19, 20). **Decisions made within the household and the family’s ability to reach care play a large part in determining neonatal outcomes.** The “three delays model”, originally developed to understand maternal deaths (21), has been adapted to assess the missed opportunities leading to neonatal deaths. The model identifies delays in: (1) identifying illness and deciding to seek care, (2) reaching the health facility, and (3) in receiving quality care once a facility is reached. **Delays recognizing illness and deciding to seek care (delay 1) are a major contributor to neonatal and child deaths, up to 80%** (18, 19, 22, 23). In research from Kenya, Uganda, and Ethiopia, mothers had difficulty identifying serious illness in newborns, and they often did not seek care outside the home even when illness was recognized (24-26). Knowledge of danger signs is associated with fewer delays in identifying illness and seeking care (27). In addition, preventative postnatal care (PNC) is underutilized. In Kenya 50% of newborns in the richest households receive PNC within 2 days after birth, and 24% of those in the poorest households (4).

Figure 4: Three delays model for neonatal care

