11.7 Data Analysis

Table 4: RCT outcomes

Outcome	Role	Indicator	Source	Timing of ascertainment	Statistical Analysis
Aim 1					
Neonatal mortality	Primary outcome	Death during 1 st 28 days of life	Questionnaire, clinic records; verbal autopsy	2 and 6 week visits, ongoing record abstraction	Cox proportional hazards
Aim 2					
Initiation of early breastfeeding	Secondary outcome	Breastfeeding in 1 st hour of life	Questionnaire	2 week visit	Poisson regression (robust standard errors)
Exclusive breastfeeding	Secondary outcome	Cessation of EBF in 1 st 6 weeks of life	Questionnaire	2 and 6 week visits	Cox proportional hazards
Thermal care	Secondary outcome	Bath in 1 st 24 hours of life	Questionnaire	2 week visit	Poisson regression (robust standard errors)
Cord care	Secondary outcome	No application of substances to cord	Questionnaire	2 week visit	Poisson regression (robust standard errors)
Maternal knowledge of neonatal danger signs	Secondary outcome	Number of the 7 danger signs or symptoms successfully named	Questionnaire	2 and 6 week visits	Poisson GEE
Appropriate care seeking	Secondary outcome	Number of clinic visits with danger sign and/or hospital admissions reported in 1 st 6 weeks	Questionnaire, clinic records	2 and 6 week visits, ongoing record abstraction	Poisson regression
Aim 3					

Depression	Secondary outcome	Score above diagnostic threshold (≥ 12) for Edinburgh Postnatal Depression Scale (70)	Questionnaire	Enrolment, 2 and 6 week visits	Poisson regression (robust standard errors)
Social support	Secondary outcome	Score using MOS Social Support Survey (71)	Questionnaire	Enrolment, 2 and 6 week visits	Linear GEE
Self-efficacy	Secondary outcome	Score using Self-efficacy in Infant Care Scale (68)	Questionnaire	Enrolment, 2 and 6 week visits	Linear GEE

For IDI analysis, two analysts will independently code transcripts to identify themes and sub-themes, coordinating analyses to create a comprehensive codebook and concept map. We will use domains identified under the IMB theory and our conceptual model to categorize participants' perceived intervention functions.

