## 1. STUDY SUMMARY AND AIMS

### Rationale:

Globally, approximately half of the estimated 6.3 million under-5 deaths occur in the neonatal period (within the first 28 days of life) and 75% of neonatal mortality occurs in the first week of life. Most neonatal deaths can be averted by existing interventions that prevent and treat neonatal illness. The “three delays framework” identifies 3 critical delays in accessing care: 1) identifying illness and the decision to seek care, 2) reaching an appropriate facility, and 3) receiving adequate care. The first delay occurs beyond the reach of the clinic and is estimated to account for up to 80% of neonatal deaths. **A critical gap exists in supporting caregivers, typically mothers, to implement essential newborn care practices (ENC) at home, identify neonatal illness when it occurs, and seek timely clinic-based care.**

Two-way (interactive) short message service (SMS) offers an efficient way for mothers to remotely interact with a healthcare worker and receive real-time education, counseling, encouragement, and decisional guidance, without placing significant burden on resource-limited health systems. **We hypothesize that two-way SMS in late pregnancy and the neonatal period can reduce neonatal mortality by 1) supporting maternal implementation of ENC (early and exclusive breastfeeding, cord care, and thermal care), 2) improving identification of neonatal danger signs and care seeking, and 3) augmenting maternal social support and self-efficacy, and reducing depressive symptoms** (Figure). We have developed a unique two-way SMS platform (Mobile WACh NEO, MWN) that rapidly and innovatively engages mothers in pregnancy and postpartum care. Our overarching aim is to determine the effect of MWN on neonatal mortality and understand the mechanisms by which this innovation impacts neonatal health. **We propose to determine the effect of MWN on neonatal mortality, ENC, care seeking, and maternal mental health in the first 6 weeks postpartum, in a 2-armed randomized controlled trial (RCT), comparing MWN SMS versus no SMS control.** Our specific aims are:

**Design:** A 2-arm, parallel assignment, unblinded, 1:1 randomized clinical trial (RCT) comparing the effects of MWN bidirectional SMS dialogue between participant and provider vs. control (no SMS) among Kenyan women.

**Population:** Pregnant women ≥14 years old and 28-36 weeks gestation.

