**Aim 2: To determine the effect of MWN SMS on maternal implementation of ENC and care seeking behavior.**

2a. To compare practices of early and exclusive breastfeeding, cord care and thermal care among mothers randomized to MWN versus control.

2b. To compare knowledge of infant danger signs and care seeking for neonatal illness among mothers randomized to MWN versus control.

*Hypothesis: Implementation of ENC, knowledge of neonatal danger signs, and clinic attendance will be higher in mothers randomized to MWN than control.*

**Aim 3: To determine the effect of MWN SMS on longitudinal maternal social support, self-efficacy and depression among mothers randomized to MWN versus control.**

*Hypothesis: Maternal self-efficacy and social support will be higher and depression will be lower among women randomized to MWN than control.*

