## 2. STUDY ENDPOINTS

Primary study endpoints:

1. **Neonatal mortality** will be defined as death of a live-born infant within 28 days of birth, based on mother's report, verbal autopsy, or clinic records.

Secondary endpoints:

1. **Early neonatal mortality** will be defined as death of a live-born infant within 7 days of birth, based on mother's report, verbal autopsy, or clinic records.
2. **Initiation of early breastfeeding** will be defined as initiation of breastfeeding within the first hour of life, based on maternal self-report at 2-week postpartum study visit.
3. **Cessation of exclusive breastfeeding** in the first 6 weeks of life will be ascertained based on maternal self-report at the 2-week and 6-week visits.
4. **Bath** in the first 24 hours of life will be ascertained based on maternal self-report at the 2-week visit.
5. **Application of substances to cord** will be ascertained based on maternal self-report at the 2-week visit.
6. **Maternal provision of Kangaroo Mother Care (KMC)** will be defined as proportion of mothers with low birth-weight or preterm babies (<2500g or <37 weeks EGA at birth) who report the baby spent any time skin-to-skin with an adult on  $\geq 10$  of the first 14 days at home.
7. **Maternal knowledge of neonatal danger signs** will be defined as the number of the 8 neonatal danger signs correctly named at 2-week and 6-week visits.
8. **Appropriate care seeking** will be defined as the proportion of illness episodes with danger signs where the infant attended the clinic and/or where the infant was hospitalized independent of neonatal danger signs in the first 18 weeks of life (study follow-up period). Illness episodes are based on maternal self-report and only include the most recent illness episode reported at the 6-week visit or 2-week visit if 6-week data is unavailable.
9. **Elevated depressive symptoms** will be defined as a score  $\geq 13$  on the Edinburgh Postnatal Depression Scale (range 0-30) at 2-week and 6-week visits.
10. **Social support score** will be defined by MOS social support score (range 0-100) at 2-week and 6-week visits.
11. **Self-efficacy** will be defined by the Karitane Parenting Confidence Scale score (range 0-45) at 2-week and 6-week study visits.

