#### c. Analyses based on continuous variables

Assuming alpha=0.0045 (Bonferroni-adjusted for 11 tests), 2-sided test, 1:1 allocation ratio, with a sample size of 2,500 per arm, and 10% attrition, we will have  $\geq 80\%$  power to detect a difference in continuous scores of 0.11: 0.50 vs. 0.61 mean clinic visits, 3.00 vs. 3.11 mean danger signs named, and 2.50 vs. 2.61 mean social support score.

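### Care seeking is compared only over reported illness episodes, a denominator the SMS may itself change, so it needs a per-infant comparison and a by-arm reporting rate beside it

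*SAP*

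**What the plan says.** SAP section 2 item 8 and section 5.3 item 9 take the proportion of danger-sign illness episodes in which the infant attended a clinic, and/or in which the infant was hospitalised whether or not danger signs were present, during follow-up of up to 18 weeks. On the episodes themselves: "Illness episodes are based on maternal self-report and only include the most recent illness episode reported at the 6-week visit", or at the 2-week visit if 6-week data are missing. The arms are compared by log-binomial regression. SAP Tables 2.1 and 5.2 also list clinic-record abstraction for this endpoint.

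The Aim 2 hypothesis in SAP section 1 concerns all randomised mothers: "knowledge of neonatal danger signs, and clinic attendance will be higher in mothers randomized to MWN than control". The SAP rationale gives as one route to lower mortality "improving identification of neonatal danger signs and care seeking". The protocol introduction says why this route matters: "Delays recognizing illness and deciding to seek care (delay 1) are a major contributor to neonatal and child deaths, up to 80"%.

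Protocol Table 4 had a count per infant, "Number of clinic visits with danger sign and/or hospital admissions reported in" the first 6 weeks, analysed by Poisson regression. SAP Table 6.1 attributes the change to a data-collection error that left care seeking recorded for the latest episode only. It does not discuss the change of denominator.

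For this endpoint the SAP plans neither an analysis over all live-born infants nor a comparison of episode reporting by arm. The intention-to-treat statement in SAP section 4 covers primary outcomes, and the best- and worst-case sensitivity analyses in SAP 5.4 cover mortality.

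**The concern.** An illness that the mother neither recognises nor reports is absent from the denominator, so it does not count as a failure to seek care. If the SMS leads mothers to recognise and report more illness, the SMS denominator grows. The planned test then asks whether care is sought equally often once an episode is reported. A gain that comes wholly from recognition cannot appear. If the additional episodes are milder and taken to care less often, the proportion falls in the arm where more infants reach care.

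What is at stake is interpretation. A null or reversed proportion could be published as no effect, or harm, on care seeking, for the step in the causal chain the trial was designed to influence. Endpoint 7 (danger signs named) does not fill the gap, because it measures knowledge and not care sought.

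**Working it through.** **The plan's own figure.** SAP section 3c is the only power statement that touches care seeking. Inputs: "Assuming alpha=0.0045 (Bonferroni-adjusted for 11 tests), 2-sided test, 1:1 allocation ratio, with a sample size of 2,500 per arm, and 10% attrition", and an effect of "0.50 vs. 0.61 mean clinic visits". The standard deviation is not stated; I assume 1.
- Evaluable per arm: 2,500 × 0.9 = 2,250.
- Detectable difference: (z for two-sided 0.0045 + z for 80% power) × SD × √(2/n) = (2.841 + 0.842) × 1 × √(2/2250) = 0.110.

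The stated 0.11 is reproduced. It is for a mean over about 2,250 infants per arm, not for a proportion of reported episodes, so it says nothing about the present endpoint.

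**Model.** The documents give no illness, reporting or care-seeking rates, so all of the following are assumptions. Let i be true danger-sign illness per infant, r the share reported, s the share of reported episodes taken to care, and x the same share among the extra episodes that only SMS mothers report.
- Planned proportion: control s; SMS [r_c·s + (r_t − r_c)·x] / r_t.
- Per infant: control i·r_c·s; SMS i·[r_c·s + (r_t − r_c)·x].

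**Case A: the SMS acts on recognition only** (i = 0.20, r = 0.60 vs 0.75, s = x = 0.80).
- Per infant: 0.20 × 0.60 × 0.80 = 0.096; 0.20 × 0.75 × 0.80 = 0.120; ratio 1.25.
- Planned: 0.80 vs 0.80; ratio 1.00.

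**Case B: the extra episodes are milder** (as A, with x = 0.40).
- Per infant: 0.20 × (0.48 + 0.06) = 0.108 vs 0.096; ratio 1.125.
- Planned: 0.54 / 0.75 = 0.72 vs 0.80; ratio 0.90.

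**Case C: the SMS acts on the decision only** (r = 0.60 in both arms, s = 0.70 vs 0.80).
- Per infant: 0.084 vs 0.096. Planned: 0.70 vs 0.80. Both ratios are 1.14.

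**Case D: the SMS prevents illness only** (i = 0.20 vs 0.15, r = 0.60, s = 0.80).
- Per infant: 0.096 vs 0.072; ratio 0.75. Planned: 0.80 vs 0.80; ratio 1.00.

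**How often each test reaches two-sided nominal 0.05.** Simulation with 2,250 infants per arm, 40,000 replicates, Wald test on the log risk ratio:

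| Case | Planned proportion | Per infant |
|---|---|---|
| A | SMS better 2% | SMS better 74% |
| B | SMS worse 64% | SMS better 26% |
| C | SMS better 77% | SMS better 29% |
| D | about 2% each way | SMS worse 83% |

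The 2% in case A is the one-sided nominal rate, because the planned endpoint is there under its own null. At 10%, 15% and 30% illness, case A gives per-infant power of 43%, 60% and 91%. With 60% vs 70% reported at 20% illness it gives 42%. At the SAP's planning alpha of 0.0045 the 74% falls to about 40%. In case B with x = 0.60 the planned test declares SMS worse 22% of the time.

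**A wider reporting gap.** With r = 0.50 vs 0.70, s = 0.80 and x = 0.40, 0.60, 0.80, 0.90, the planned ratio is 0.86, 0.93, 1.00, 1.04. The per-infant ratio is 1.20, 1.30, 1.40, 1.45.

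**Hospitalisation limb.** Take the same reporting gap with x = 0.60, and add admissions without danger signs in 1%, 3% or 5% of infants per arm, always counted as success. The planned ratio is 0.93, 0.93 and 0.94; the per-infant ratio is 1.27, 1.22 and 1.18. The limb dilutes the pattern but does not remove it.

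**The case against.** A reader might infer that the planned endpoint is invalid, or biased against the SMS, and should be replaced by a per-infant one. The documents do not support that, for five reasons.

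- **The planned quantity fits a stated aim.** Aim 2b in SAP section 1 is to compare care seeking for neonatal illness, and a proportion among illness episodes is a natural reading of it. The first delay includes the decision to seek care as well as recognition. When the SMS acts on the decision (case C), the planned proportion is the more powerful test, 77% against 29%. When it acts on both (60% vs 70% reported, 70% vs 80% taken to care), the two perform similarly, 79% and 89%.
- **Differential reporting is not established.** The questionnaire wording is not in the documents. If staff asked about each symptom in turn, reporting a fever or poor feeding need not depend on knowing that it is a danger sign.
- **A per-infant measure can mislead in the same way.** Protocol section 15 already expects that control infants may have more visits if their mothers practise less newborn care. In case D the per-infant test declares SMS worse 83% of the time.
- **The data are limited.** A per-infant yes/no still relies on maternal report, and an infant taken to care for an earlier episode but not for the latest one could be coded as no.
- **The denominator is not confined to danger-sign episodes.** Hospitalisations enter regardless of danger signs.

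All five stand, and they rule out replacement. They do not answer the narrower point: the planned proportion alone cannot show whether recognition changed how many infants reached care, and nothing planned beside it would reveal that. The severity comparison in Protocol section 15 is triggered only if controls have more visits or hospitalisations, so it does not address who enters the denominator.

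**Conclusion.** The concern holds as a gap in what accompanies the endpoint. The planned comparison is conditional on a reported episode, a post-randomisation event that the SMS may affect, and so does not by itself test the Aim 2 hypothesis about all randomised mothers. If reporting differs by arm, it can be null (1.00 against a per-infant ratio of 1.25) or reversed (0.90 against 1.125) while more SMS infants reach care. If the extra episodes are taken to care more often than the rest, it still favours the SMS but understates the gain (1.04 against 1.45). If reporting and illness are equal, the problem vanishes. These figures rest on assumed rates and show what is possible, not what is likely. It would go too far to say that the trial will miss or invert an effect, because the documents give nothing from which to judge size or direction. This is a low-cost improvement to one of 11 secondary endpoints.

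**What to change.** In SAP section 2 item 8 and section 5.3 item 9, keep the episode-based proportion and its log-binomial model. Add beside it:

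- (a) the proportion of live-born infants with follow-up who had a reported danger-sign illness taken to a clinic, or a hospital admission, compared between arms by the same log-binomial model;
- (b) the proportion of infants with follow-up who had any reported danger-sign episode, by arm.

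State that an effect, or no effect, on care seeking will be concluded only from the three read together. A higher (b) in the SMS arm with a flat or lower planned proportion points to a change in who enters the denominator. A lower (a) together with a lower (b) is compatible with less illness or less reporting, and is not in itself evidence of worse care seeking. Label (a) and (b) as supportive, and record the addition and its date in SAP Table 6.1.

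The cost is a few lines of SAP text, two derived yes/no variables and two rows in Table 5.3, with no new data collection. The limits of (a) should be stated with it: it falls if the SMS prevents illness, depends on maternal report, and captures the most recent episode only. For those reasons it accompanies the planned comparison and does not replace it.

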**Table 2.1 Summary of primary and secondary endpoints**

Outcome	Indicator	Source	Timing
Primary outcome			
Neonatal mortality	Death during 1 st 28 days of life	Questionnaire, clinic records; verbal autopsy	2 and 6 week visits, clinic record abstraction
Secondary outcomes			
Early neonatal mortality	Death during 1 st 7 days of life	Questionnaire, clinic records; verbal autopsy	2 and 6 week visits, clinic record abstraction
Initiation of early breastfeeding	Breastfeeding in 1 st hour of life	Questionnaire	2 week visit
Exclusive breastfeeding	Cessation of EBF in 1 st 6 weeks of life	Questionnaire	2 and 6 week visits
Thermal care	Bath in 1 st 24 hours of life	Questionnaire	2 week visit
Home provision of KMC	Any duration of skin-to-skin care on $\geq 10$ of the first 14 days at home, among low birthweight or preterm infants	Questionnaire	2 week visit

Cord care	No application of substances to cord	Questionnaire	2 week visit
Maternal knowledge of neonatal danger signs	Number of the 8 danger signs or symptoms successfully named	Questionnaire	2 and 6 week visits
Appropriate care seeking	Proportion of illness episodes with danger signs where the infant attended the clinic and/ or where the infant was hospitalized regardless of danger signs reported during study follow-up	Questionnaire, clinic records	2 and 6 week visits, ongoing record abstraction
Depression	Score above diagnostic threshold ( $\geq 13$ ) for Edinburgh Postnatal Depression Scale	Questionnaire	Baseline, 2 and 6 week visits
Social support	Score using MOS Social Support Survey	Questionnaire	Enrollment, 2 and 6 week visits
Self-efficacy	Score using Karitane Parenting Confidence Scale	Questionnaire	Baseline, 2 and 6 week visits

### 3. SAMPLE SIZE CONSIDERATIONS

Our endpoints will be compared between study arms using 3 types of statistical tests: comparison of proportions achieving the endpoint, comparison of hazard of the end-point by survival analysis, and comparison of continuous outcomes (see section 5.3). Secondary analyses will be adjusted for multiple comparisons using the Benjamini Hochberg method with a false discovery rate of 5%. In the power calculations below we use a conservative estimate with Bonferroni adjustment as an indication of the upper limit of our detectable effect sizes.

#### a. Analyses based on survival analysis

Assuming alpha=0.05, 2-sided test, 1:1 allocation ratio, with a sample size of 2,500 per arm, and 10% attrition, we will have  $\geq 80\%$  power to detect a Hazard Ratio (HR) of 0.53 in neonatal mortality, assuming mortality of 23 per 1000 births in the control arm. Assuming alpha=0.0045 (Bonferroni-adjusted for 11 tests) and 2-sided test, we will have  $\geq 80\%$  power to detect a difference of 90.0% vs. 93.1% continued exclusive breastfeeding to 6 weeks.

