**Table 3.1 Summary of detectable differences**

Indicator	Outcomes (control)	Minimum detectable difference		
		Outcomes (intervention)	Absolute difference	Relative difference
Neonatal mortality per 1000 births 	25.0	13.8	11.2	0.55
	23.0	12.2	10.8	0.53
	20.0	10.0	10.0	0.50
Initiation of BF within 1h; EBF for 6 weeks 	90.0%	93.1%	3.1%	1.03
	80.0%	84.2%	4.2%	1.05
Application of substances to cord; Bath within 24h 	40.0%	45.4%	5.4%	1.14
	50.0%	55.5%	5.5%	1.11
Provision of KMC 	30.0%	43.7%	13.7%	1.46
	25.0%	38.2%	13.2%	1.53
Number of clinic visits in first 6 weeks 	0.50	0.61	0.11	1.22
	1.00	1.11	0.11	1.11
Number of danger signs correctly named 	3.00	3.11	0.11	1.04
	5.00	5.11	0.11	1.02
Maternal depression 	19.0%	14.5%	4.5%	0.76
Maternal social support score; Maternal self-efficacy score (max 4.0) 	2.50	2.61	0.11	1.04
	3.50	3.61	0.11	1.03

 $\alpha$ =0.05, Adjusted  $\alpha$ =0.0045,  $\beta$ =0.8, 2-sided tests

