**Table 5.2 Summary of statistical analyses**

Outcome	Indicator	Timing	Statistical Analysis
Primary outcome			
Neonatal mortality	Death during 1 st 28 days of life	2 and 6 week visits, clinic record abstraction	Log-binomial regression
Secondary outcomes			
Early neonatal mortality	Death during 1 st 7 days of life	2 and 6 week visits, clinic record abstraction	Log-binomial regression
Initiation of early breastfeeding	Breastfeeding in 1 st hour of life	2 week visit	Log-binomial regression
Exclusive breastfeeding	Cessation of EBF in 1 st 6 weeks of life	2 and 6 week visits	Cox proportional hazards
Thermal care	Bath in 1 st 24 hours of life	2 week visit	Log-binomial regression
Cord care	No application of substances to cord	2 week visit	Log-binomial regression
Home provision of KMC	Any duration of skin-to-skin care on ≥10 of the first 14 days at home, among low birthweight or preterm infants	2 and 6 week visits	Log-binomial regression
Maternal knowledge of neonatal danger signs	Number of the 8 danger signs or symptoms successfully named	2 and 6 week visits	Poisson GEE
Appropriate care seeking	Proportion of illness episodes with danger signs where the infant attended the clinic and/or where the infant was hospitalized regardless of danger signs reported in study follow-up	2 and 6 week visits, ongoing record abstraction	Log-binomial regression
Depression	Score above diagnostic threshold (≥13) for Edinburgh Postnatal Depression Scale	Baseline, 2 and 6 week visits	Log-binomial GEE
Social support	Score using MOS Social Support Survey	Enrollment, 2 and 6 week visits	Linear GEE
Self-efficacy	Score using Self-efficacy in Infant Care Scale	Baseline, 2 and 6 week visits	Linear GEE

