## 5.4 INTERIM ANALYSIS

An interim analysis for neonatal mortality will be performed using O'Brien-Fleming boundaries for benefit and harm when 50% of expected person time has been accrued. The plot below shows the standardized z-value boundaries for interim monitoring.

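### SAP 3a states mortality power for a hazard ratio with no interim look; at the SAP's own attrition the planned log-binomial risk-ratio test has about 77–79%, not 80% or more

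*SAP*

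**What the plan says.** SAP section 3a places neonatal mortality among the survival analyses. Its inputs are "Assuming alpha=0.05, 2-sided test, 1:1 allocation ratio", "with a sample size of 2,500 per arm, and 10% attrition" and "assuming mortality of 23 per 1000 births in the control arm". From these it claims at least 80% "power to detect a Hazard Ratio (HR) of 0.53 in neonatal mortality". The matching row of Table 3.1, under "Neonatal mortality per 1000 births", reads "23.0 12.2 10.8 0.53". The other two mortality rows are 25.0 vs 13.8 and 20.0 vs 10.0.

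The analysis now planned is different. SAP 5.3 item 1 compares the proportion of live-born infants who die by day 28, and Table 5.2 gives the method as "Log-binomial regression". SAP Table 6.1 dates the change from Cox regression to 8 October 2020. The SAP's interim analysis section adds O'Brien-Fleming "boundaries for benefit and harm when 50% of expected person time has been accrued".

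The three mortality rows match those in the sample size table of protocol 11.4, which was built on 2,510 per arm and a primary outcome that protocol Table 4 assigns to Cox regression. The other rows of the SAP table did move: the adjusted alpha went from 0.0055 to 0.0045, the tests from 9 to 11, and a kangaroo-care row was added.

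**The concern.** The power statement describes a different effect measure and test from those the trial will use, at a significance level with no interim look. The denominator also differs. The calculation takes randomised women less 10%, whereas the analysis set is live-born infants. The SAP's missing-data section describes the 10% as loss to follow-up between enrolment and the 6-week visit. Protocol 11.6.i foresees pregnancy losses, but section 3 makes no stated allowance for them.

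The stake is the headline claim for the primary endpoint. A reader cannot match the stated power to the planned analysis, and needs to know whether 80% still holds once the two are aligned.

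**Working it through.** **Inputs.** Two-sided alpha 0.05, 1:1 allocation, 2,500 per arm and 10% attrition (SAP 3a) give n = 2,500 × 0.90 = 2,250 per arm. Event rates are those of SAP Table 3.1.

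**Step 1: reproduce the stated figure (23.0 vs 12.2).** Expected deaths D = 2,250 × (0.0230 + 0.0122) = 79.2. Schoenfeld: power = Φ(|ln HR| × √D / 2 − 1.960).
- HR 0.53: 0.635 × 8.90 / 2 = 2.825, so power = Φ(0.865) = 80.6%.
- HR implied by the two risks, ln(1 − 0.0122) / ln(1 − 0.0230) = 0.528: power 81.2%.

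The statement of at least 80% therefore reproduces under this formula.

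**Step 2: the planned test.** Wald test of the log risk ratio:
- Variance = (1 − p1)/(n p1) + (1 − p2)/(n p2) = 0.977/51.75 + 0.9878/27.45 = 0.0189 + 0.0360 = 0.0549, so SE = 0.234.
- |ln(0.0122/0.0230)| = 0.634, and 0.634/0.234 = 2.707.
- Power = Φ(2.707 − 1.960) = 77.2%.

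Exact power sums the two binomial probabilities over all outcomes in which the test rejects. All three rows, at 2,250 per arm:

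| Deaths per 1000 | Schoenfeld | Wald formula | Exact Wald | Exact score |
|---|---|---|---|---|
| 25.0 vs 13.8 | 80.0% | 76.5% | 78.0% | 78.2% |
| 23.0 vs 12.2 | 81.2% | 77.2% | 79.2% | 79.2% |
| 20.0 vs 10.0 | 81.8% | 77.1% | 79.4% | 79.6% |

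**Step 3: where the gap comes from.** Schoenfeld uses variance 4/D = 4/79.2 = 0.0505, as if deaths split evenly between arms. At this effect they split about 52 to 27, and the variance is 0.0549. Freedman's formula gives 78.6%. In 60,000 simulated single-stage trials the powers were: log-rank 79.4%, Cox Wald 79.1%, score test of proportions 79.3%, Wald risk ratio 79.2%. The choice of test hardly matters.

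**Step 4: the interim look (23.0 row).** The boundary plot is not visible in the text, so two standard forms were tried for one look at 50% information. Lan-DeMets O'Brien-Fleming gives |z| = 2.963 then 1.969. The classical form gives 2.797 then 1.977.
- Overall power by the Wald formula: 77.1% (Lan-DeMets) or 76.9% (classical).
- By the score formula: 78.5% or 78.4%.
- By two-stage simulation: 78.6–79.5%.

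The look costs about 0.1–0.3 points by formula and at most about 0.6 in simulation.

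**Step 5: live births (illustration only).** The documents give no loss rate. With the Lan-DeMets look, an assumed loss of 1%, 2%, 3% or 5% gives 76.7–78.1%, 76.3–77.7%, 75.8–77.3% or 75.0–76.4% (Wald to score formula).

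**Step 6: detectable effect at 80%.** Exact Wald at a final critical value of 1.977, before any pregnancy loss, gives 13.5, 12.0 and 9.8 per 1000 for control rates of 25, 23 and 20. The risk ratios are about 0.54, 0.52 and 0.49.

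**The case against.** The strongest objection concerns cause. A reader might infer that replacing Cox by log-binomial regression, together with the interim look, cost the trial its 80%. Step 3 shows otherwise: a Cox or log-rank test on the same data also has about 79%, and the look costs less than 1 point. Nor is the stated figure an arithmetic slip, since it reproduces. Both points stand. They explain the gap but do not restore 80%, which neither test reaches at 2,250 per arm.

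A reader might also conclude that the design cannot deliver 80%. That rests on applying all 10% attrition to this endpoint. The 10% runs to the 6-week visit, whereas the endpoint closes at day 28. The SAP rationale puts 75% of neonatal deaths in the first week, and deaths are also found through record review. If only 5% were missing (2,375 per arm, an assumption), exact power for the 23.0 row at 1.977 would be 80.6% (Wald) or 81.3% (score). At 8% missing (2,300) it would be 79.3% or 80.0%. This also stands: the shortfall is conditional on the SAP's own attrition input, which is nevertheless the one behind its claim.

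Finally, pregnancy loss has a direction but no documented size. The SAP does not say whether the 10% includes it, and twins or deaths recorded before drop-out could offset it. No figure for it can be presented as a result.

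The objection that nothing practical changes is fair. The detectable rate in the 23.0 row moves only from 12.2 to 12.0 per 1000.

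**Conclusion.** The inconsistency is real and minor. Section 3a and the mortality rows of Table 3.1 describe a hazard ratio at 0.05 with no interim, while the planned primary analysis is a log-binomial risk ratio among live births with one O'Brien-Fleming look. On the SAP's own inputs the planned test has about 77–79% power in all three rows. The shortfall is about 0.5 to 3 points, or 3.5 at most (25.0 row, Wald formula). The exact figures are the better guide and put it at 2 points or less before the interim.

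The result assumes 2,250 evaluable infants per arm and one of the two standard O'Brien-Fleming forms. The protocol's 2,510 per arm, less 10%, gives 77.3–78.7% for the 23.0 row (Lan-DeMets, Wald to score formula), so it does not change the conclusion. The documents do not support calling the trial materially underpowered or blaming the change of test.

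**What to change.** - Move neonatal mortality out of section 3a and into the comparison of proportions, with the effect expressed as a risk ratio.
- Recompute the three mortality rows of Table 3.1 for the log-binomial test. State either about 77–79% power for the present differences or the detectable risk ratios of about 0.54, 0.52 and 0.49 for control rates of 25, 23 and 20 per 1000.
- Name the formula or method used, and use the actual final O'Brien-Fleming boundary.
- State the expected number of live births, and whether the 10% covers pregnancy loss as well as loss to follow-up.
- Record the change in SAP Table 6.1 as a correction of the planning text.

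The cost is a few lines of SAP text and a slightly less favourable stated figure. Sample size, conduct and the analysis itself do not change.
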